## **6.6 Dose Modification**

No dose modifications are allowed during the study.

## **6.7 Intervention After the End of the Study**

There is no planned intervention following the end of the study.

# **7 DISCONTINUATION OF STUDY INTERVENTION AND PARTICIPANT DISCONTINUATION/WITHDRAWAL**

## **7.1 Discontinuation of Study Intervention**

It may be necessary for a participant to permanently discontinue (definitive discontinuation) study intervention. Participants who permanently discontinue study intervention prior to Week 12 will have an EDV as described in [Table 2](#). If study intervention is permanently discontinued, the participant should remain in the study, ie, continue to participate in scheduled study visits and evaluations.

Note that discontinuation from study intervention is NOT the same thing as a withdrawal from the study.

At each visit, participants will be instructed to contact the investigator immediately if rash or skin reaction has developed. If maculopapular rash CTCAE Grade 1, 2, or 3 has developed, the participant must be permanently discontinued from study intervention and AstraZeneca medical staff must be informed.

- CTCAE Grade 1: Macules/papules covering < 10% body surface area with or without symptoms (eg, pruritus, burning, tightness)
- CTCAE Grade 2: Macules/papules covering 10% to 30% body surface area, with or without symptoms (eg, pruritus, burning, tightness); limiting instrumental activities of daily living (refer to preparing meals, shopping for groceries or clothes, using the telephone, managing money, etc); rash covering > 30% body surface area with or without mild symptoms
- CTCAE Grade 3: Macules/papules covering > 30% body surface area, with moderate or severe symptoms; limiting self-care activities of daily living (refer to bathing, dressing and undressing, feeding self, using the toilet, taking medications, and not bedridden)

If the participant develops a rash or skin reaction that is not considered a maculopapular rash but is a generalized rash/skin reaction or is considered to be an SAE, the participant must be permanently discontinued from the study intervention and AstraZeneca medical staff should

be informed.

Further information and rash/skin reaction evaluation guidance is provided in Appendix [E 5](#).

Participants may also be discontinued from the study intervention in the following situations:

- Participant decision - The participant is at any time free to discontinue treatment, without prejudice to further treatment
- Lost to follow-up
- Pregnancy in a female participant
- AE or other safety reasons as judged by the investigator and/or sponsor, where continued treatment may put the participant at undue risk
- Development of uncontrolled and clinically significant **CCI** as judged by the investigator
- Severe non-compliance with the CSP
- Elevations in liver tests corresponding to possible DILI (Appendix [F 8](#) for details)

Data to be collected at the time of intervention discontinuation and follow-up and any further evaluations that need to be completed are noted in [Table 2](#).

### **7.1.1      Temporary Discontinuation**

Every attempt should be made to maintain participants on the study intervention during the course of the study. If the study intervention has been interrupted, it should be re-introduced as soon as, in the opinion of the investigator, the participant is able to re-start study treatment.

Note related to AESI skin reactions (including maculopapular rash): In the event of maculopapular rash CTCAE Grade 1, 2, or 3, or any other generalized rash/skin reaction or serious rash/skin reaction, study intervention should be permanently discontinued. At each visit, participants will be instructed to stop the study intervention and contact the investigator immediately if rash or skin reaction has developed. After the participant has been seen by the study doctor or designee and the skin reaction is not considered a maculopapular rash CTCAE Grade 1, 2, or 3, or any other generalized rash/skin reaction or serious rash/skin reaction, the study treatment can be restarted.

### **7.1.2      Rechallenge**

Participants who have temporarily discontinued study intervention can resume treatment as soon as, in the opinion of the investigator, the participant is able to re-start study treatment and the participant wishes to resume. No minimum time period is necessary before treatment can resume.

If a participant develops maculopapular rash CTCAE Grades 1, 2, or 3 or any other generalized rash/skin reaction or serious rash/skin reaction, study intervention should be permanently discontinued.

## 7.2 Participant Withdrawal from the Study

- A participant may withdraw from the study at any time at his/her own request or may be withdrawn at any time at the discretion of the investigator for safety, behavioral, compliance, or administrative reasons. This is expected to be uncommon.
- A participant who considers withdrawing from the study must be informed by the investigator about modified follow-up options (eg, telephone contact, a contact with a relative or treating physician, or information from medical records).
- At the time of withdrawal from the study, if possible, an EDV should be conducted, as shown in [Table 2](#) for data to be collected at the time of study withdrawal and follow-up and for any further evaluations that need to be completed.
  - The participant will discontinue the study intervention and be withdrawn from the study at that time.
- If the participant withdraws consent for disclosure of future information, the sponsor may retain and continue to use any data collected before such a withdrawal of consent.
- If a participant withdraws from the study, it should be confirmed if he/she still agrees for existing samples to be used in line with the original consent. If he/she requests withdrawal of consent for use of samples, destruction of any samples taken and not tested should be carried out in line with what was stated in the informed consent and local regulation. The investigator must document the decision on use of existing samples in the site study records and inform the Global Study Team.
- The reason for participant withdrawal should be recorded in the eCRF.

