#### **AE Variables**

The following variables will be collected for each AE:

- AE (verbatim)
- The date and time when the AE started and stopped
- Maximum intensity
- Maximum CTCAE grade for maculopapular rash
- Whether the AE is serious or not
- Investigator causality rating against the IP (yes or no)
- Action taken with regard to IP
- AE caused participant's withdrawal from study (yes or no)
- Outcome

In addition, the following variables will be collected for SAEs:

- Date AE met criteria for SAE
- Date investigator became aware of SAE
- AE is serious due to
- Date of hospitalization
- Date of discharge
- In case of fatality:

- Probable cause of death
- Date of death
- Autopsy performed
- Causality assessment in relation to study procedure(s)
- Causality assessment to other medication

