## 9.4.2 Pharmacodynamics

### 9.4.2.1 Primary Endpoint

The primary pharmacodynamic endpoint for this study is change from baseline to Week 12 in log-transformed ALT.

The null hypothesis of no decrease in ALT comparing AZD4831 (mitiperstat) to placebo will be tested versus the alternative hypothesis of a decrease in ALT in favor of AZD4831 (mitiperstat) to placebo using a one-sided test at 5% significance level, assessed through a treatment policy estimand. The endpoint will be analyzed in a mixed effects linear model with participant as random effect, treatment, visit and treatment-by-visit interaction as fixed effects, and baseline as covariate. Data will be log-transformed before analyses, and results will be back-transformed to describe relative change versus placebo in value at end of treatment relative to baseline. Furthermore, data will also be analyzed as individual percental change, that is  $(\text{value at time } t - \text{value at baseline})/(\text{value at baseline})100\%$ , in a similar mixed effects model but without log transformation of data.

- **Treatment:** Treatment with 5 mg AZD4831 (mitiperstat) compared to placebo, administered in addition to optimal background therapy for co-morbidities
- **Population:** FAS
- **Endpoint:** Change from baseline in log-transformed ALT
- **Intercurrent events:** Intercurrent events will be ignored (treatment policy strategy) and potential missing data imputed
- **Population-level summary:** Relative change versus placebo in value at end of treatment relative to baseline

Any missing baseline ALT values will be imputed based on existing baseline values of FAS participants using PROC MI MCMC, disregarding the treatment group. For postbaseline missing ALT values, a distinction in the imputation will be made between non-monotone and monotone missing data. Monotone missing data are defined as missing data that constitute the end participant follow-up, while non-monotone missing data means that there are observations made after the missing time point. Any non-monotone missing data will be replaced using PROC MI MCMC while monotone missing data will use PROC MI regression. The imputation model will include timepoint, baseline value, and treatment group. More details will be described in the SAP.

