4.1.3 Protocol Deviations

4.1.3.1 Definitions and Derivations

Important protocol deviations (IPDs) are defined as protocol deviations which may significantly affect the completeness, accuracy and/or reliability of the study data, or which may significantly affect a patient's right, safety or well-being. They will include (but are not limited to):

- Inclusion criteria deviations
- Exclusion criteria deviations
- Discontinuation criteria for study product met but subject not withdrawn from study treatment
- Discontinuation criteria for overall study withdrawal met but subject not withdrawn from study

- Investigational Product (IP) Deviation
- Excluded medications taken
- Deviations related to study procedure
- Other important deviation

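### Protocol 7.1 and 7.2 give different follow-up for overlapping reasons, so an investigator withdrawal can cost a Week 12 ALT that the treatment-policy estimand needs

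*Protocol*

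**What the plan says.** - **Protocol 7.1 (stopping drug).** "If study intervention is permanently discontinued, the participant should remain in the study, ie, continue to participate in scheduled study visits and evaluations". The section lists safety reasons and severe non-compliance among the grounds for stopping drug, and notes that stopping drug is different from leaving the study.
- **Protocol 7.2 (leaving the study).** A participant "may be withdrawn at any time at the discretion of the investigator for safety, behavioral, compliance, or administrative reasons". The section adds "This is expected to be uncommon". On follow-up it says "At the time of withdrawal from the study, if possible, an EDV should be conducted", and then "The participant will discontinue the study intervention and be withdrawn from the study at that time".
- **Protocol 9.4.2.1 (primary estimand, ALT).** "Intercurrent events will be ignored (treatment policy strategy) and potential missing data imputed". Section 9.4.2.2 applies the same strategy to Pro-C3, and says that a randomized participant may leave the study but not the analysis.
- **SAP 3.3.2 (visit windows).** Visits are assigned by study day. The Week 12 window is Day 78 to Day 105.
- **SAP 4.1.1.1 (disposition).** Study discontinuation is defined as withdrawn consent, loss to follow-up or death. Investigator decision is not among the categories.
- **SAP 4.1.3.1 (important deviations).** One listed category is "Discontinuation criteria for overall study withdrawal met but subject not withdrawn from study".

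**The concern.** A treatment-policy estimand for Week 12 ALT needs the Week 12 measurement whether or not the participant is still on drug. Section 7.1 is written to secure it. Section 7.2 opens a second route, at the investigator's discretion and partly for the same reasons, that ends measurement as well as treatment. Safety and compliance can be grounds for stopping drug without being grounds for no longer drawing an ALT sample.

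Withdrawals for these reasons can be related to treatment and tolerability. What is at stake is informative missingness: the participant stays in the full analysis set, but the Week 12 value comes from a model instead of from a sample that could have been taken. The SAP deviation category points the same way, because it treats failure to withdraw as the error, while the protocol defines no criteria for overall study withdrawal. Section 7.2 grants discretion and sets no criteria.

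**Working it through.** **1. The two routes compared**

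| | 7.1 | 7.2 |
|---|---|---|
| Safety | listed | listed |
| Compliance | severe non-compliance listed | listed |
| Behavioral, administrative | not listed as such | listed |
| Study drug | stops | stops |
| Scheduled visits | continue | end |
| Week 12 ALT and Pro-C3 | collected at Visit 8 | not secured |

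Drug stops on either route. Only the follow-up differs.

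**2. Does anything in 7.2 secure a Week 12 value?**
- The early discontinuation visit takes place only where possible. SAP Table 1 puts it in the same row as Visit 8, but the SAP assigns a visit by its day. A visit before Day 78 is not a Week 12 value; one on Days 78 to 105 can be.
- Modified follow-up is offered to a participant who is considering withdrawal. The examples (telephone, a relative or treating physician, medical records) do not provide the scheduled central-laboratory ALT described in Protocol 8.2.5.
- Imputation supplies a modelled value and does not recover the measurement.

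**3. The plan's sample size, and whether power is threatened**

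Inputs (Protocol 9.2): 25% decrease, SD 0.50 on the log scale, one-sided 5%, power at least 80%, 10% missing, 45 per arm.

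- δ = −ln(0.75) = 0.2877.
- n = 2 × (1.645 + 0.842)² × 0.50² / 0.2877² = 37.4, so 38 per arm. 38 / 0.90 = 42.2, so 43. The plan's 45, and the SAP's 40 evaluable, are reproduced to within 2.
- Power at 45 per arm by share missing (normal approximation, treating missing values as lost): 0% 86.1%; 5% 84.5%; 10% 82.7%; 15% 80.8%; 20% 78.7%. It falls below 80% only above about 17% missing (about 15% with the noncentral t).

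Uncommon withdrawals within the 10% allowance therefore do not threaten power.

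**4. What a withdrawal could do to the estimate (illustration only)**

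Assume that a share f of the active arm is withdrawn, that those participants have no drug effect at Week 12, and that they are imputed as if still on drug. The documents support none of these as fact. The treatment-policy decrease is then 1 − exp(−0.2877 × (1 − f)), while the analysis would target 25.0%.

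| f | Treatment-policy decrease | Gap (points) |
|---|---|---|
| 2% | 24.6% | 0.4 |
| 5% | 23.9% | 1.1 |
| 10% | 22.8% | 2.2 |
| 15% | 21.7% | 3.3 |

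One participant of 45 (f = 2.2%) gives 1 − exp(−0.2877 × 44/45) = 24.5%, a gap of about 0.5 points.

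For scale, with 40 per arm the standard error is 0.50 × √(2/40) = 0.112. The 95% interval around a 25% decrease is 1 − exp(−0.2877 ± 1.96 × 0.112), or about 7% to 40%.

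**The case against.** **Withdrawals are meant to be rare.** Section 7.2 says so, Section 7.1 states the default of staying in the study, and 9.4.2.2 separates stopping drug from leaving the trial. This stands and limits the weight of the point. No criterion or limit accompanies the expectation, however, so it secures no data.

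**Rash as the driver.** A reader might infer that rash stops will be lost through 7.2 and that the effect will be overstated by a calculable amount. Protocol 4.3 gives 5 mg rash rates of 1/27 and 2/12, so 45 × 1/27 = 1.7 and 45 × 2/12 = 7.5 stops (pooled 3/39: 3.5). If all were withdrawn and imputed as on-drug, the formula above gives 24.2% and 21.3% against 25.0%, gaps of 0.8 and 3.7 points. The arithmetic is right, but the documents do not support the premise. Sections 7.1, 7.1.1 and 7.1.2 handle rash as discontinuation of study intervention, with visits continuing under 7.1, and nothing sends these participants through 7.2. The same section of the protocol reports no rash below 15 mg in the Phase I multiple-dose study.

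**Imputation may reflect treatment status.** SAP Appendix 7.2 requires indicators for the last visit on treatment and for treatment through all 12 weeks, and its monotone step names two separate seeds. This suggests, without proving, that participants off drug are imputed differently. The key text is blacked out, and SAP 4.2.1 is not in the available text. So the illustration in step 4 cannot be offered as the trial's bias. A model that used off-drug status would still depend on participants who stopped drug and stayed, which is the information that 7.2 withdrawals remove.

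**Weak supporting items.** The eCRF field on whether an adverse event caused study withdrawal does not show who decided; the participant may have. The SAP deviation category is a reporting label, and its handling sits in a separate Protocol Deviation Plan that is not available. Both are fair. The category still refers to criteria that the protocol does not contain.

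**Investigator discretion protects participants.** Removing it entirely would go too far. This stands, and the change below keeps exceptions.

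**Conclusion.** The inconsistency is real. For safety and compliance reasons, 7.1 and 7.2 prescribe different follow-up and the choice is left to the investigator. Nothing in the available text secures a Week 12 ALT or Pro-C3 after a 7.2 withdrawal, although the estimand for both endpoints is treatment policy.

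The consequence is limited to this: each such withdrawal exchanges an observable value for an imputed one. The number of withdrawals is not given and is expected to be small. The direction and size of any bias cannot be stated while the imputation rule is partly blacked out. Power is not threatened within the planned 10%. This is a cheap improvement to the quality of the primary data and does not show that the primary result would be biased.

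**What to change.** 1. **Protocol 7.2.** Reconcile it with 7.1. Where the reason is safety, behavior or compliance, handle the case as discontinuation of study intervention with continued scheduled visits, or at least the Visit 8 ALT and Pro-C3 sample. Keep exceptions for a participant who withdraws consent or cannot be reached, and for cases where continued visits are themselves judged unsafe or are administratively impossible, such as site closure.
2. **SAP 4.1.3.1.** Remove the category on criteria for overall study withdrawal, or align it with the protocol, which defines no such criteria.

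No rule on when study drug is stopped changes; only follow-up after the stop does.

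**Cost.** A few extra visits for participants already off drug, of the kind 7.1 already asks for, and a reminder to sites. The SAP serves three regional protocols (SAP section 1), so the wording must be aligned in all three. Protocol amendments need ethics committee and regulatory approval (Protocol Appendix D 1), so the change is best carried in an amendment made for other reasons as well.

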## 7.3 Lost to Follow Up

A participant will be considered lost to follow-up if he or she repeatedly fails to return for scheduled visits and is unable to be contacted by the study site.

The following actions must be taken if a participant fails to return to the clinic for a required study visit:

- The site must attempt to contact the participant and reschedule the missed visit as soon as possible and counsel the participant on the importance of maintaining the assigned visit schedule and ascertain whether or not the participant wishes to and/or should continue in the study.

- Before a participant is deemed lost to follow up, the investigator or designee must make every effort to regain contact with the participant (where possible, 3 telephone calls and, if necessary, a certified letter to the participant's last known mailing address or local equivalent methods). These contact attempts should be documented in the participant's medical record.
- Should the participant continue to be unreachable, he/she will be considered to have withdrawn from the study.
- Site personnel, or delegated third party, will attempt to collect the vital status of the participant within legal and ethical boundaries for all participants randomized, including those who did not get IP. Public sources may be searched for vital status information. If vital status is determined as deceased, this will be documented and the participant will not be considered lost to follow-up. Sponsor personnel will not be involved in any attempts to collect vital status information.

Discontinuation of specific sites or of the study as a whole are handled as part of [Appendix D](#).

#### 7.4 Study Stopping Criteria

In the event of any of the following criteria being met, the clinical trial would be stopped if confirmed with the DRC.

- Any one death considered related to AZD4831 (mitiperstat) by the DRC.
- A difference of 2 patients experiencing SAEs considered related to AZD4831 (mitiperstat) by the DRC as compared to placebo.
- One Hy's Law case on AZD4831 (mitiperstat) (That is: AST or ALT  $\geq 3 \times$  ULN **together with** Total Bilirubin  $\geq 2 \times$  ULN, where no other reason, other than the IMP, can be found to explain the combination of increases).
- Five patients who experience the following categories of rash/skin reaction leading to permanent discontinuation: CTCAE Grade 2 maculopapular rash, CTCAE Grade 3 maculopapular rash, other generalized rash/skin reaction not considered maculopapular, or other rash/skin reaction not considered maculopapular that is considered as an SAE; these would also need to be considered related to AZD4831 (mitiperstat) by the DRC.

### 8 STUDY ASSESSMENTS AND PROCEDURES

- Study procedures and their timing are summarized in [Table 2](#). Protocol waivers or exemptions are not allowed.

- Immediate safety concerns should be discussed with the sponsor immediately upon occurrence or awareness to determine if the participant should continue or discontinue study intervention.
- Adherence to the study design requirements, including those specified in [Table 2](#), is essential and required for study conduct.
- All screening evaluations must be completed and reviewed to confirm that potential participants meet all eligibility criteria. The investigator will maintain a screening log to record details of all participants screened and to confirm eligibility or record reasons for screening failure, as applicable.
- Procedures conducted as part of the participant's routine clinical management (eg, blood count) and obtained before signing of the ICF may be utilized for screening or baseline purposes provided the procedures met the protocol-specified criteria and were performed within the time frame defined in [Table 2](#).
- The maximum amount of blood collected from each participant over the duration of the study, including any extra assessments that may be required, will not exceed 300 mL. Repeat or unscheduled samples may be taken for safety reasons or for technical issues with the samples.

## 8.1 Efficacy Assessments

ALT will be used as a surrogate non-invasive biomarker of hepatocellular injury ([Table 8](#)). The primary endpoint is change in ALT from baseline and over placebo to Week 12.

## 8.2 Safety Assessments

Planned time points for all safety assessments are provided in [Table 2](#). AEs based on examinations and tests are described in Section [8.3.5](#).

### 8.2.1 Medical History

Complete medical history will include history and current medical conditions past or present cardiovascular disorders; respiratory, gastrointestinal, renal, hepatic, neurological, endocrine, lymphatic, hematologic, immunologic, dermatological, psychiatric, genitourinary, or any other diseases or disorders; drug and surgical history; and history of alcohol and tobacco use.

The AUDIT questionnaire to assess alcohol use habits will be completed at screening only ([Table 2](#)). The AUDIT questionnaire should be administered by the investigator using the latest version, downloaded from <https://auditscreen.org>. A sample is provided in [Appendix B](#). The results will be used for determining participant eligibility (Section [4.4](#)).

